4.3 Biosafety: N/A

4.4 Stem Cells: N/A

4.5 Fetal Tissue: N/A

5.0 Procedures Involved

5.1 Study Design:

Single institution, prospective, randomized, unblinded superiority study of renal transplant surgery participants, with no history of previous transplant, comparing a resistive blanket warming system (Hotdog (U102); Augustine Surgical, Inc., Eden Prairie, MN, USA) to a forced air warming system (Bair Hugger, Model 635; 3M Medical, St. Paul, MN, USA).

A randomization schedule will be developed using permuted block randomization with blocks of size 2, 4, 6, and 8 assuming 1:1 allocation within each block. Data will be analyzed using an intention-to-treat protocol.

5.2 Study Procedures:

The study will involve two arms: a resistive blanket warming system arm and a forced air warming system arm. Both devices will be set to warm the patient at each device's maximum setting at the beginning and throughout the case. The hotdog's maximum setting is 39C and the Bair Hugger's maximum setting is 41C.

The patient will be randomized to either the FAWS or RBWS before arrival to the operating room. Depending on which arm they have randomized to, the

MEDICAL PROTOCOL (HRP-590)

PROTOCOL TITLE: Comparison of normothermia maintenance between resistive blanket and forced air warming systems in renal transplant surgery

VERSION DATE: V43 January June 6, 2022

participant will be placed on either the underbody FAWS or the RBWS. An upper body FAWS will be placed on top of the patient prior to incision but is only to be utilized if normothermia cannot be achieved during the surgery with either device. The warming system that the patient is randomized to will be set up on the table before the participant is brought to the OR and transferred to the operating room table. The main warming device will be turned on once the patient is positioned on the operating table. The CRNA's will be involved in the placement of the blankets. Surgeons, OR Nurse Managers, and CRNA's will be informed by research team regarding patient's involvement in the study.

After the needed standard monitors for surgery have been placed, general anesthesia will be induced and maintained with patient's hemodynamics and other vitals maintained per standard care (no additional measurements beyond standard of care which is recorded in EPIC). Standard anesthetic care of the participant will occur for the duration of the surgery.

Patient core temperature will be measured with a nasopharyngeal temperature probe. The patient's temperature will be monitored and recorded for the duration of surgery with the selected warming system. Vital signs, including continuous blood pressure, heart rate, oxygen saturation, and end-tidal carbon dioxide, will be monitored and recorded in Epic as is routine with all anesthetics performed. Our primary outcome variable is the NP temperature as recorded at the end of the surgery.

After the surgery, the patient will be transported to the PACU in a timely fashion. Temperature measurement in the PACU will be standardized with skin temperature probes (3M Spot-On) that will be placed on the forehead prior to leaving the operating room. If there is an unexpected delay in transporting the patient to the PACU, that will be documented and the temperature upon arrival to PACU will not be valid.

Data to be collected about participants and the source records that will be used to collect those data:

From Epic:

- Age
- Sex
- MRN
- Height
- Weight
- BMI
- Date of procedure
- Procedure performed

MEDICAL PROTOCOL (HRP-590)

PROTOCOL TITLE: Comparison of normothermia maintenance between resistive blanket and forced air warming systems in renal transplant surgery

VERSION DATE: V43 January June 6, 2022

- Nasopharyngeal temperature throughout surgery (every minute)
- Time at warming system being switched (resistive blanket or forced air)
- Time when patient reaches 37°C
- Time at OR departure
- Time sign-out from PACU prior to transfer to regular nursing floor
- Blood product volume administered to patient (red blood cells, fresh frozen plasma, platelets, and cryoprecipitate)
- Recorded incidence of rescue warming used for when patient's temperature is at 35.5°C (requiring rescue means the need to turn on the additional forced air warming device that may be due to severe hypothermia and uncontrolled bleeding)

Individually Identifiable Health Information: See above

HIPAA Agreement: Attached

5.3 Study Duration:

Individual Subject Participation Duration: Patients will be in the study for their scheduled procedure and for 1 hour following their procedure. Duration of the surgical procedure, is typically 2-5 hours depending on the surgery required. Following the study, participants will not be approached at any time, for any reason as it pertains to their study participation.

Total Study Duration (all Participants): approximately 1 year

Total Study Duration Including Data Analysis: about 14 months

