An additional upper body FAWS will be placed on top of the patient prior to surgery for rescue purpose and will only be utilized if normothermia cannot be achieved during the surgery with the device the patient is randomized to. During periods when the participant will need to be warmed, the additional upper body device will be switched on to generate heat in addition to the main warming device.

The Hotdog blanket will be donated by the manufacturer. The Anesthesiologist will train CRNA staff on the use of this device and will maintain continual communication with the CRNA Lead to ensure staff is aware of the study and receives proper training. A staff member from the Anesthesiology Research Office will be in charge of the inventory of the donated blankets, stored in the core of the OR department. A research team member will bring the Hotdog device to the OR prior to surgery, if the patient is randomized to Hotdog and will make sure there is a rescue Bairhugger in the OR for all patients. After the surgery, OR staff

MEDICAL PROTOCOL (HRP-590)

PROTOCOL TITLE: Comparison of normothermia maintenance between resistive blanket and forced air warming systems in renal transplant surgery

VERSION DATE: V43 January June 6, 2022

will do their normal process of cleaning supplies, including the Hotdog, and will put the device back in the OR core.

The HotDog resistive blanket warming system is FDA approved and available for use in surgery.

4.2 Device Handling:

During the study, the participant will be randomized to lay on top of either the underbody forced air warming system or resistive blanket, this will be the main warming device for the patient. An additional upper body device will be placed on patients in case rescue warming is needed at the discretion of the anesthesiologist. All staff participating in patient care will be instructed that a patient's body temperature of 35.5 degrees Celsius or lower is the threshold for intervention. During periods when the participant will need to be warmed, the additional upper body device will be switched on to generate heat in addition to the main warming device.

Forced air warming blankets are single patient use only. The resistive blankets are reusable. In between use, the resistive blankets will be cleaned and disinfected per manufacturer's instructions.

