13.0 Risks to Participants

13.1 Foreseeable Risks:

None beyond those routinely associated with transplant surgery and anesthesia and temperature management. Thermal injury to the skin (with or without actual burns) is listed as a risk for all warming systems that contact the skin (including both forced air and resistive blankets) but such events are exceedingly rare when the equipment is used as intended. We will use the devices according to the manufacturer's recommendations of operating the devices.

Participation in research may involve a loss of privacy due to the nature of the questions that are asked and/or data collected. However, records will be handled as confidentially as possible. No identifying information will be used in any report or publications that may result from this study. All study records will be kept in a UMN box and REDCap which are secure databases. Paper records will be kept in locked cabinets in locked rooms only accessible to study staff.

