15.0 Statistical Considerations

15.1 Data Analysis Plan:

1. Our primary outcome variable is the patient's temperature at the end of surgery.

2. Secondary outcome variables also include:

- AUC of time versus temperature curves;
- temperatures at set points during operative period;
- blood loss volumes

All continuous measures will be summarized with mean (standard deviation) or median (interquartile range) based upon evaluation of normality using statistical tests (e.g., Shapiro-Wilk) and graphical representation (e.g., histograms, boxplots). Categorical measures will be summarized by count (percent).

The secondary outcomes are continuous measures and will be compared using two-sided two-sample t-tests for unadjusted comparisons of the groups. Adjusted comparisons will use linear regression models to account for potential confounders that may affect the outcome based upon the clinical literature.

Safety outcomes of interest include the incidence of hyperthermia, rescue warming, and incidence of thermal injury. These are categorical variables and will be compared using the χ^2 test or Fischer's exact test for unadjusted comparisons and with logistic regression models to account for potential confounders.

Final data set will be assessed for missing data, depending on rate of missing data, we will use statistical methods to account for missing data

15.2 Power Analysis:

A mean difference of 0.5°C in patient temperatures between the two devices would be clinically meaningful. However, limited data exists, so a range of standard deviations were explored to examine the different sample sizes needed at 80% and 90% power (assuming a two-sided two-sample t-test with $\alpha=0.05$).

Power	SD	N per Group	Overall N
0.8	0.25	6	12

MEDICAL PROTOCOL (HRP-590)

PROTOCOL TITLE: Comparison of normothermia maintenance between resistive blanket and forced air warming systems in renal transplant surgery

VERSION DATE: V43 January June 6, 2022

	0.5	17	34
	0.75	37	74
	1	64	128
0.9	0.25	7	14
	0.5	23	46
	0.75	49	98
	1	86	172

We will take a conservative approach by enrolling 49 patients per group (98 patients total). As this is a minimal risk study, we expect to an 80% enrollment rate; we will approach (98 + 20% = 123 patients). In 2019, the University of Minnesota Medical Canter performed approximately 240 renal transplants for a total of ~200 eligible patients or ~16 eligible patients/month; 100 total patients approached/16 eligible patients per month = 6.25 months.

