17.0 Confidentiality

17.1 Data Security:

Only the core study team (PI, co-PI, and support personnel) will have access to PHI and data during the initial collection process. Intraoperative recording of relevant events for the study will be recorded on paper or in REDCap on an IPAD in the operating room, which will be imported into REDCap and saved in box in a way that de-identifies the data. Intraoperative subject vitals will also be exported

MEDICAL PROTOCOL (HRP-590)

PROTOCOL TITLE: Comparison of normothermia maintenance between resistive blanket and forced air warming systems in renal transplant surgery

VERSION DATE: V43 January June 6, 2022

from EPIC into spreadsheet format and be saved on research computers in a de-identified fashion. Data collected by the VitalIDB software package will be done in real-time to a hospital-owned computer for use dedicated to the research team, and will have no patient identifiers except for date and time of the data collected, and subject number, and will be merged into the spreadsheet containing the data imported from EPIC. Data will then be processed on these computers that are dedicated solely to the research team. A separate spreadsheet of PHI (patient name, MRN, date of surgery, procedure) will be compiled of study subjects in the case additional information needs to be collected or verified. The spreadsheet with PHI and data spreadsheets will be saved in an encrypted format in BOX. All computers that are dedicated to the research team will not leave the research site (Fairview hospitals, University of Minnesota) and be secured in a locked office when not in use. Transmission of data will be performed within approved University storage and transfer modalities (encrypted e-mail, local network drives, etc.). Original consent documents and data collected on paper, which will include patient information, will be stored in a locked cabinet in a locked research office, accessible only to the core study team.

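### Section 5.2 keeps both warming devices at maximum for the whole case with no upper-temperature exception, although hyperthermia is a safety outcome: a minor patient-safety gap that one clause closes

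*Combined protocol and SAP*

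**What the plan says.** All references are to the combined protocol and SAP.

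- **Device setting (5.2).** Each device runs at its "maximum setting at the beginning and throughout the case". "The hotdog's maximum setting is 39C and the Bair Hugger's maximum setting is 41C". No condition for lowering the setting follows.
- **Action temperature (4.2, also 3.2 and 5.2).** Staff are told that a "body temperature of 35.5 degrees Celsius or lower is the threshold for intervention". The action is to switch on a second, upper-body forced-air blanket. The other patient temperatures carry no action: 36°C defines hypothermia for an endpoint (3.2), and 37°C is a time to be recorded (5.2).
- **Safety outcomes (15.1).** "Safety outcomes of interest include the incidence of hyperthermia, rescue warming, and incidence of thermal injury". No temperature defines hyperthermia.
- **General protections.** 5.2 says "Standard anesthetic care of the participant will occur for the duration of the surgery" and keeps vital signs under standard care. 13.1 commits to the "manufacturer's recommendations of operating the devices". 12.1 lets the treating physicians withdraw a patient for safety. None of these gives an upper temperature.
- **Context.** The trial is unblinded and analysed by intention to treat (5.1, 15.3). The primary outcome is nasopharyngeal (NP) temperature at the end of surgery, and NP temperature is extracted every minute (5.2).

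**The concern.** Read literally, 5.2 goes on heating a patient who already has one of the trial's own safety outcomes. A clinician who turns the device down acts correctly but departs from 5.2, and 18.1 has the principal or co-investigator check each record for adherence to the protocol. All staff are given one common threshold on the low side and none on the high side.

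Two consequences follow for the results. First, providers who know the arm would each choose their own turn-down temperature. The device setting is the intervention, so this could move the primary outcome. Second, an incidence of hyperthermia cannot be scored without a cut-off, and one chosen after the arms have been compared could be chosen to suit the result.

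**Working it through.** **The gap.** This part is a matter of reading. Every patient temperature in the plan was listed with its action: 35.5°C adds heat, 36°C defines an endpoint, 37°C is a recorded time. None reduces heat. The figures 39C and 41C are device settings, so they do not show that patients will become hyperthermic.

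**The plan's own figure.** For a difference of 0.5°C, SD 0.75, two-sided α = 0.05 and 90% power (15.2), the exact two-sample t-test needs 48.26 per arm, rounded up to 49. This matches the plan. Power at 49 per arm is 0.904.

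**Assumptions for the rest.** The plan gives no expected mean temperatures, so three pairs were assumed, other arm/stronger arm: 35.75/36.25, 36.0/36.5 and 36.5/37.0°C. End-of-surgery temperature is taken as normal with SD 0.75 and 49 patients per arm. Turning down is modelled as holding the temperature at the limit L.

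**How many patients would be warm.** Expected number above c in one arm: 49 × [1 − Φ((c − μ)/σ)]. Totals of 98:

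| Means (°C) | Above 37.5°C | Above 38.0°C |
|---|---|---|
| 35.75/36.25 | 0.48 + 2.34 = 2.8 | 0.55 |
| 36.0/36.5 | 1.11 + 4.47 = 5.6 | 1.3 |
| 36.5/37.0 | 4.47 + 12.37 = 16.8 | 5.6 |

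Section 15.2 explores SDs from 0.25 to 1. At 36.0/36.5 the number above 37.5°C is 0.0, 1.2, 5.6 and 11.0 (3.27 + 7.77) for SD 0.25, 0.5, 0.75 and 1.

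**What a limit does to the difference.** With a = (L − μ)/σ, a limit lowers an arm's mean by σ[φ(a) − a(1 − Φ(a))]. At the warmest means, 36.5/37.0:

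- Common 38.0°C: stronger arm a = 1.333, lowered 0.0318; other arm a = 2.0, lowered 0.0064. Net loss 0.025, difference 0.475°C.
- Common 37.5°C: stronger arm a = 0.667, lowered 0.1133; other arm a = 1.333, lowered 0.0318. Net loss 0.082, difference 0.418°C.
- Unequal, stronger arm at 37.5 and other at 38.0: 0.1133 − 0.0064 = 0.107 lost, difference 0.393°C.

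Power uses the variances after the limit and an unequal-variance noncentral t:

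| Means (°C) | Common 38.0 | Common 37.5 | Stronger 37.5, other 38.0 |
|---|---|---|---|
| 35.75/36.25 | 0.498°C, 90% | 0.488°C, 90% | 0.485°C, 90% |
| 36.0/36.5 | 0.495°C, 90% | 0.475°C, 90% | 0.469°C, 89% |
| 36.5/37.0 | 0.475°C, 90% | 0.418°C, 89% | 0.393°C, 82% |

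Of the 0.107°C lost in the worst cell, 0.082 comes from the 37.5°C limit itself and 0.107 − 0.082 = 0.025 from the arms being treated differently.

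**A wider SD.** With SD 1 at the warmest means, the same formula gives a loss of 0.0833 − 0.0293 = 0.054°C for a common 38.0°C limit and 0.1978 − 0.0833 = 0.115°C for 37.5°C.

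**The case against.** The strongest reply is that 5.2 is a standardisation instruction. The same section keeps vital signs and anesthetic care at the usual standard, 13.1 defers to the manufacturer, 12.1 and 12.3 allow withdrawal or termination for safety, and 18.1 provides adverse-event review with power to halt enrolment. No anesthesiologist would read 5.2 as forbidding a turn-down. Nor do the documents suggest a warm population: 4.1 describes limited air circulation under the patient, rescue planning is for cold patients, and 8.2 excludes infection and thyroid dysfunction. Most of this stands, and it keeps the point minor. It does not supply a common limit or a cut-off.

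Four stronger readings are tempting, and the documents do not support them.

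- **That the plan orders staff to overheat patients.** The general protections are also written rules and let staff act.
- **That the primary comparison is biased.** Turn-down temperatures that differ by arm are conjecture. Only the assumed warmest means, with the stronger arm limited earlier, bring power down to 82%. Nor is the opposite order shown to be harmless: limits exactly 0.5°C apart match the assumed gap between the means, so the difference stays at 0.500°C by construction.
- **That device changes would go unrecorded.** The 5.2 data list already includes the time at which the warming system is switched. Whether that covers a reduced setting is only a matter of detail.
- **That overheated patients would be lost from the analysis.** The statement in 16.3 about withdrawn participants answers a question on access to records, while 5.1 and 15.3 specify intention to treat.

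**Conclusion.** The point holds as a minor, cheap patient-safety improvement. Section 5.2 states a rule without the exception that the trial's own safety outcome calls for, and the hyperthermia outcome cannot be scored as written. It does not make the trial unsafe or the primary analysis invalid.

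The gap itself rests on the text alone. Its consequence for the primary outcome rests on assumptions that the documents cannot confirm: the arm means, normality, and the hold-at-limit model. Under these, with SD 0.75, the part due to having no common limit is small, 0.025°C even in the least favourable case examined. How often patients would become warm cannot be judged from the plan.

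**What to change.** 1. In 5.2, state that each main device stays at its maximum unless NP temperature reaches a pre-stated upper limit, the same in both arms (for example 38.0°C, or 37.5°C if the investigators prefer), at which the device is turned down or off. Add that this is neither a deviation nor a withdrawal and that the patient stays in the intention-to-treat analysis.
2. In 15.1, fix the temperature that counts as hyperthermia and score it from the every-minute NP trace for all patients. Do this before any data are compared, which means before the interim review in 18.2. The cut-off need not equal the turn-down limit.

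The cost is a few sentences, because the NP trace is already extracted. The real downside is that warming is no longer strictly maximal in warm patients. The modelled losses favour 38.0°C over 37.5°C if statistical cost alone decides, but the choice of limit is clinical and belongs to the investigators.

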5.4 Use of radiation: N/A

5.5 Use of Center for Magnetic Resonance Research: N/A

6.0 Data and Specimen Banking

6.1 Storage and Access: The storage and access to study data will be HIPAA compliant

6.2 Data: Data will be entered in REDCAP and stored in UMN Box Secure storage. Signed Informed Consents in paper form will be stored in the Anesthesia Research Office.

6.3 Release/Sharing: Data will be stored internally within the research group. Data will not be shared with the company providing the RWBS.

7.0 Sharing of Results with Participants

7.1 Individual participant results will not be shared. High-level summary study results may be publicly available in a publication of research results in a scientific journal.

7.2 Sharing of genetic testing: N/A

8.0 Study Population

MEDICAL PROTOCOL (HRP-590)

PROTOCOL TITLE: Comparison of normothermia maintenance between resistive blanket and forced air warming systems in renal transplant surgery

VERSION DATE: V43 January June 6, 2022

8.1 Inclusion Criteria:

- Eighteen (18) years to 90 years old
- Undergoing elective renal transplantation

8.2 Exclusion Criteria:

- Previous surgery involving organ transplantation or nephrectomy. These patients are at higher risk of blood loss, making temperature regulation subject to more variables outside our control.
- ~~End stage renal disease with decreased or no urine output from normal.~~
- Previous upper extremity amputations
- Ongoing sepsis or other infection
- Thyroid dysfunction
- Emergency surgery
- Refusal of consent to participate in study
- Pregnancy

8.3 Screening:

First, potential participant's chart in Epic will be accessed to ensure they are not "Research Opt Out" (will not be approached by research team). Participants will be seen in the preoperative holding area before surgery. Participants will be identified before the procedure either by participating anesthesiologists or transplant surgeons when an organ is available and a renal transplant surgery is scheduled. An approved member of the research team will be notified when the case is scheduled and the recipient has been sent for. This individual will then discuss the nature of the study and obtain consent. In all cases, a member of the anesthesia team will be available (either in person or via phone) to directly answer any questions that cannot be addressed by a non-physician member of the team.

9.0 Vulnerable Populations

9.1 Vulnerable Populations:

Population / Group	Identify whether any of the following populations will be targeted, included (not necessarily targeted) or excluded from participation in the study.
Children	Excluded from

MEDICAL PROTOCOL (HRP-590)

PROTOCOL TITLE: Comparison of normothermia maintenance between resistive blanket and forced air warming systems in renal transplant surgery

VERSION DATE: V43 January June 6, 2022

	Participation Excluded from Participation
Pregnant women/fetuses/neonates	Excluded from ParticipationExcluded from Participation
Prisoners	Excluded from ParticipationExcluded from Participation
Adults lacking capacity to consent and/or adults with diminished capacity to consent, including, but not limited to, those with acute medical conditions, psychiatric disorders, neurologic disorders, developmental disorders, and behavioral disorders	Excluded from ParticipationExcluded from Participation
Non-English speakers	Included/Allowed to ParticipateIncluded/Allowed to Participate
Those unable to read (illiterate)	Excluded from ParticipationExcluded from Participation
Employees of the researcher	Excluded from ParticipationExcluded from Participation
Students of the researcher	Excluded from ParticipationExcluded from Participation
Undervalued or disenfranchised social group	Included/Allowed to ParticipateIncluded/Allowed to Participate
Active members of the military (service members), DoD personnel (including civilian employees)	Included/Allowed to ParticipateIncluded/Allowed to Participate

MEDICAL PROTOCOL (HRP-590)

PROTOCOL TITLE: Comparison of normothermia maintenance between resistive blanket and forced air warming systems in renal transplant surgery

VERSION DATE: V43 January June 6, 2022

Individual or group that is approached for participation in research during a stressful situation such as emergency room setting, childbirth (labor), etc.	Included/Allowed to Participate Included/Allowed to Participate
Individual or group that is disadvantaged in the distribution of social goods and services such as income, housing, or healthcare.	Included/Allowed to Participate Included/Allowed to Participate
Individual or group with a serious health condition for which there are no satisfactory standard treatments.	Excluded from Participation Excluded from Participation
Individual or group with a fear of negative consequences for not participating in the research (e.g. institutionalization, deportation, disclosure of stigmatizing behavior).	Included/Allowed to Participate Included/Allowed to Participate
Any other circumstance/dynamic that could increase vulnerability to coercion or exploitation that might influence consent to research or decision to continue in research.	Excluded from Participation Excluded from Participation

9.2 Additional Safeguards:

Language: Patients with any primary language other than English will be considered for inclusion, so long as there is a professional interpreter available for the consent process and other aspects of the study. The study does not target participants with any specific language. A short form, if available, will be used if the subject is non-English speaking.

Undervalued social group: Research staff will not be asking about this social group, however vulnerability will not be increased by participating.

Military: Research staff will not be asking about this social group, however vulnerability will not be increased by participating.

Stressful Situation: Given that participants are approached in the pre-op area prior to surgery, this may be a stressful situation. Extra caution will be taken as to not coerce the potential participant. They will be encouraged to ask questions of the research team or PI/Sub-PI and will be given adequate time to discuss with

MEDICAL PROTOCOL (HRP-590)

PROTOCOL TITLE: Comparison of normothermia maintenance between resistive blanket and forced air warming systems in renal transplant surgery

VERSION DATE: V43 January June 6, 2022

their support. Individuals who are noticeably nervous or stressed at that time will not be consented.

Disadvantaged group: Research staff will not be asking about this social group, however vulnerability will not be increased by participating.

Fear of Participating: Research staff will not be asking about this social group, however vulnerability will not be increased by participating.

